## 1. Purpose of Study and Background

### 1.1 Purpose

The purpose of EQUIPED is to test and evaluate a care quality improvement intervention featuring use of consensus decisional guidance for the medical management of diabetes (DM) patients with Alzheimer's and other forms of dementia (ADRD) in primary care at NYU Langone Health. This quality improvement program will include provider (PCP) workflow enhancements supported by a panel manager (PM) for workflow support, electronic health record (EHR) decision support and feedback, and PCP collaborative learning.

It will test hypotheses about whether care based on explicit standards for DM medical management for people with ADRD will: **H1**) Improve patient symptoms and quality of life while maintaining expected clinical outcomes; **H2**) decrease patient and caregiver management burden and improve care quality based on patient/caregiver preferences; **H3**) (secondary) decrease specialty, ED and hospital utilization.

In order to test and evaluate this program, we will conduct a pragmatic randomized controlled trial (RCT) and evaluate it using mixed methods (surveys and interviews) in 20 NYU Langone Health clinics with the enrollment goal of 500 patients with diagnosed DM and ADRD in the intervention (INT) and control (CON) group (1,000 total).

If EQUIPED demonstrates that patients and family caregivers who receive this quality improvement program achieve established goals for diabetic care in addition to fewer dementia-related symptoms, less caregiver burden and stress, and fewer DM-related adverse events, potentially avoidable and costly utilization may also decrease. This best practice approach could then be widely disseminated to other clinical practices.

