### 1.2 Specific Aims

Specific Aims of the R33 Enhanced Quality In Primary Care for Elders with Diabetes-ADRD (EQUIPED-ADRD) are:

- 1) Implement and evaluate a pragmatic trial in a large healthcare system using cluster randomization, and the practice change framework, that will: manage people with co-occurring DM and ADRD according to the guidelines developed to test our hypotheses and identify additional patients with cognitive impairment and inappropriate DM management.
- 2) Test whether EQUIPED-ADRD will increase the proportion of intervention patients who are in desirable glycemic and blood pressure ranges compared to control patients.
- 3) Test whether the EQUIPED-ADRD intervention will improve dyad perception of care quality and reduce treatment burden.
- 4) Test whether dementia symptoms will deteriorate less in intervention subjects compared to controls.

**Exploratory Aim.** Test whether intervention subjects will use fewer health care services than controls and will have less cognitive decline associated with desired changes in glycemic and blood pressure control.

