## 3. Subject Population

### 3.1 Total Number of Subjects and Sites

We will randomize the **20 largest NYU Langone Health primary care practices**, 9 Intervention (**INT**) clinics and 9 control (**CON**) clinics. We will enroll **1,000** patients (and their caregivers)  $\geq 65$  with diabetes (DM) and Alzheimers disease and other forms of dementia (ADRD) from these practices based on the Inclusion and Exclusion criteria below. As stated in inclusion and exclusion criteria, patients must have a caregiver who will also be enrolled. The patient and caregiver are referred to as a "dyad."

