### **INT Clinics:**

In the INT clinics we will introduce the panel manager (PM) to all clinic staff and develop processes for interaction. The PM will work with INT clinic providers to individualize communication methods between the PCP and PM. Each month INT clinic providers will get a list of eligible patients who have appointments with them in the coming month - those with diagnoses of DM-ADRD and those 75 and older with DM who are out of range for HbA1c or BP. This process gives providers monthly reminders about the ongoing quality improvement study and is a more intensive form of QI intervention than provided to CON clinics.

Because this is a pragmatic trial, the clinical team and a project-funded PM will deliver the intervention, fitting it as closely as possible into usual clinical workflow. The clinical team includes PCPs, occasional APNs and PAs (who function as PCPs), RN's, MA's, office staff, and clinic onsite administration. The PM will be part of the team; PMs providing chronic disease self-management support (usually telephonic) are clinic team members in many healthcare systems.

We will assign two PMs to 9 randomly selected INT clinics. Each PM will have 4.5 INT clinics and will engage and focus on their first clinics in a randomly ordered step-wise fashion working within 1-2 clinics over a focused 3-month period before moving on to the next 1-2 clinics for 3 months, then the last 1-2 clinics for 3 months. Our preliminary data suggests 20-50 patients per INT clinic with DM-ADRD  $\geq 65$  years; and about an equal number with DM without ADRD who will screen positive for cognitive impairment, most of whom are  $\geq 75$  years and identified by HbA1c/BP over or under treatment, or identified by provider referral, which we will allow. With 9 INT clinics, given our preliminary data about patient numbers, each PM will have an anticipated 300 dyads. PMs can engage about 33 patients/month, making initial 300 patient/CG contact in 9 months.

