## 7. Data Analysis

We will begin all analyses with descriptive summary statistics and graphical displays of all variables. Continuous variables will be summarized with means, medians, standard deviation and interquartile range; categorical variables will be summarized with frequencies. We will assess the balance by treatment assignment of patients in the INT and CON clinics with respect to demographic and clinical characteristics (e.g., age, gender, Charlson Index, socioeconomic status, baseline TBQ, etc.) using standard tests (t-tests, Wilcoxon rank-sum tests, and  $\chi^2$  tests as appropriate). Any factors that appear to be unbalanced by treatment assignment will be considered as adjustment factors in the primary analyses. All hypothesis testing will be two-sided and conducted using a significance level of 0.05.

The primary outcome of 'on target' HbA1C values will be measured for each patient as a binary indicator. The primary analysis will use a generalized linear mixed model approach, with a logit link, for the probability of being 'on target.' The treatment group (CON vs INT) will be the primary fixed effect of interest; we will also include the practice as a random effect to accommodate clustering of patients within clinics. We will also explore non-parametric methods such as quantile regression or other rank-based approaches. As noted above, randomization should obviate the need for any additional covariate adjustment, but we will explore whether adjustment for clinic-level characteristics (e.g., clinic size) and provider-level characteristics (e.g., provider demographics and panel size) is necessary. We will use standard assessments of goodness-of-fit, including residual plots, to evaluate the models. Finally, in addition to reporting the treatment difference in terms of the odds ratio from the logistic regression, we will report absolute risk difference as well.

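### With about 18 randomised clinics, the plan should not rely on randomisation to make covariate adjustment unnecessary; the primary HbA1c model needs a prespecified baseline covariate

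*Combined protocol and SAP*

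**What the plan says.** Section 1.2 describes a "pragmatic trial in a large healthcare system using cluster randomization". Section 3.1 says that the "20 largest NYU Langone Health primary care practices" will be randomised, but the same sentence then lists 9 intervention "clinics and 9 control" clinics, which makes 18. Section 4 (INT Clinics) says "We will assign two PMs to 9 randomly selected INT clinics". No section mentions stratification, matching, minimisation or constrained allocation.

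Section 7 specifies a logistic mixed model for the binary on-target HbA1c outcome, with treatment as the fixed effect of interest and practice as a random effect. On covariates it says three things:

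- "randomization should obviate the need for any additional covariate adjustment".
- Adjustment for clinic-level and provider-level characteristics will be explored.
- Balance between patients in the two arms will be tested with t, Wilcoxon and chi-square tests, and factors that look unbalanced will be considered for the primary analyses.

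No covariate is fixed in advance and nothing defines unbalanced. HbA1c is collected at month 0 when available (Section 5.4, Measures), but baseline on-target status is not named in the primary model.

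**The concern.** Randomisation balances well when many units are randomised. Here the units are 18 clinics, not 1,000 patients, so a sizeable chance difference between the two sets of clinics is likely. The plan meets this with a premise that so few units cannot support and a route to adjustment that is decided after the data are seen.

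The planned balance tests do not repair this. They treat patients as independent, so for anything that clusters by clinic they do not measure imbalance on the scale on which it arose. With no rule for what counts as unbalanced, the covariates of the primary model are a choice made late. At stake are the precision of the HbA1c contrast and how far a reader can trust the single allocation that was drawn.

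**Working it through.** The documents give no power, ICC, on-target rate or imbalance figure, so there is no stated result to reproduce.

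**Inputs from the documents.** 9 clinics per arm (10 if Section 3.1's 20 is right); 500 patients per arm (Section 1.1); two-sided 0.05 (Section 7). **Assumptions.** On-target rate p = 0.5; ICC 0.01 to 0.10; shares of variance explained as shown. Calculations are on the risk-difference scale, as an approximation to the planned logistic model.

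1. *Chance imbalance in one clinic characteristic.* The SD of the standardised arm difference is sqrt(2/k). For k = 9 it is sqrt(2/9) = 0.471, and P(difference > 0.5 SD) = 2 x Phi(-0.5/0.471) = 0.289. For k = 10: SD 0.447, probability 0.264. For 500 individually randomised patients per arm the SD would be sqrt(2/500) = 0.063.

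2. *At least one of three characteristics.* If independent, 1 - (1 - 0.289)^3 = 0.640. Enumerating all C(18,9) = 48,620 allocations on simulated covariates gives 0.66. A feature held by 9 of the 18 clinics splits 6:3 or worse in 35% of allocations.

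3. *Share of the contrast's variance that lies between clinics.* Between: 2p(1-p) x ICC/9. Within: 2p(1-p) x (1-ICC)/500. At ICC 0.02 these are 0.00111 and 0.00098, so 53% is between clinics. At ICC 0.01, 0.05 and 0.10 the share is 36%, 75% and 86%.

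4. *Shift from a 0.5 SD imbalance.* 0.5 x sqrt(R2 x ICC x p(1-p)), where R2 is the share of between-clinic variance that the characteristic explains. For R2 of 30-50%: 1.9-2.5 points at ICC 0.02 and 3.1-4.0 points at ICC 0.05.

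5. *Type I error.* In 20,000 simulated trials (cluster-level t test, no adjustment), error over all allocations was 4.8% (ICC 0.02, R2 30%) and 5.0% (ICC 0.05, R2 50%). Among allocations with imbalance above 0.5 SD it was 8% and 11%.

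6. *Effect of constraining the allocation.* Keeping the best-balanced 10% (4,862 of 48,620) on three characteristics cuts the imbalance SD from 0.47 to 0.17, and no retained allocation exceeded 0.5 SD in the simulated sets. Stratifying on one characteristic at its median cuts its chance of exceeding 0.5 SD from 30% to 14%.

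7. *Effect of adjustment on the detectable difference (80% power).* Unadjusted at ICC 0.02: (2.120 + 0.865) x sqrt(0.5 x (0.02/9 + 0.98/500)) = 2.985 x 0.0457 = 13.6 points. Each of q clinic-level terms costs one of 16 degrees of freedom, and chance imbalance inflates the variance by about 1 + q/(15 - q).

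| Model, ICC 0.02 | Detectable difference (points) |
|---|---|
| Unadjusted | 13.6 |
| Two clinic-level terms, together explaining 30% of between-clinic variance | 13.6 |
| One clinic-level term explaining 30% | 13.0 |
| One clinic-level term explaining nothing | 14.2 |
| Patient-level baseline, explaining 30% between and 10% within clinics | 12.2 |
| Patient-level baseline, explaining 50% between and 25% within clinics | 10.7 |
| Patient-level baseline, explaining nothing between and 10% within clinics | 13.3 |

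Two-term row: 3.013 x sqrt(0.5 x (0.02 x 0.7/9 + 0.98/500) x 1.154) = 3.013 x 0.0450 = 13.6. At ICC 0.01 the same two terms make matters slightly worse (11.7 to 12.0). At ICC 0.05 they help a little (18.2 to 17.4).

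**The case against.** **The plan does not rule out adjustment.** A reader might infer that Section 7 assumes balance and stops there. It does not: it checks balance, will consider unbalanced factors in the primary analyses and will explore clinic-level terms. That stands. The criticism is that this adjustment is chosen after the event and without a rule. Nor does choosing by test necessarily inflate error: with one covariate and a fixed clinic-level test, simulated error was 4.1-4.5%. The plan, however, fixes neither the covariates nor the rule, and its tests are at patient level.

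**Unrestricted cluster randomisation is valid.** A reader might also infer that the primary comparison is biased. The documents do not support that. The practice random effect is there to carry between-clinic variation into the standard error, and step 5 shows near-nominal error over all allocations (with a small-sample t reference, which the plan does not mention). The harm is lost precision and conditional inaccuracy.

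**The absence of balancing is an inference from silence.** The quoted Section 4 sentence is about staffing by panel managers. A balanced method may have been used and recorded elsewhere. This stands: the method is unstated, not shown to be unrestricted.

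**The constrained-allocation remedy may come too late, and compulsory clinic-level terms may not help.** The COVID questionnaire is to be completed at baseline or follow-up (Section 5.4), which suggests that dyads may already have been enrolled when it was added. Step 7 confirms that two clinic-level terms can give nothing at low ICC. Both points stand, and they are why the main fix is the patient-level baseline covariate.

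**Conclusion.** The concern holds in a limited form. With 9 clinics per arm and no balancing described, the expectation that randomisation removes the need for adjustment is unsafe: 29% chance of a difference above 0.5 SD on a given clinic characteristic, and 64-66% on at least one of three. Reconciling 18 with 20 clinics does not change this (26% for one characteristic at 10 v 10).

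Those probabilities rest only on the number of clinics and roughly normal characteristics, with the three taken as independent. The translation into HbA1c points rests on assumed values of the ICC, the on-target rate and the variance explained, and should be read as a range. The plan should be changed because a better primary model is available from data already being collected, not because the planned test is invalid.

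**What to change.** 1. In Section 7, delete the statement that randomisation makes adjustment unnecessary and the selection of covariates by balance test. Name patient-level baseline HbA1c on-target status as a fixed covariate in the primary mixed model. State a rule for missing baseline values, and define baseline for patients who join when the sample is refreshed, since their clinic's programme may already be running.
2. If clinics are not yet allocated, use covariate-constrained randomisation: for example, draw at random from the best-balanced 10% of allocations on clinic size, Medicare/Medicaid share and baseline on-target proportion, and include the balancing variables in the model. The first two are already in Table 1; the third would have to be built from Epic.
3. If clinics are already allocated, state the method used and add at most one clinic-level term (clinic size), fixed before outcome data are seen.
4. Reconcile 20 practices with 9 + 9 in Section 3.1.

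**Cost.** Protocol wording and, for item 2, a short program. Each clinic-level term uses one of about 16 degrees of freedom and may give no gain at low ICC. The patient-level term uses no clinic-level degree of freedom and costs almost nothing. It makes the odds ratio conditional on baseline status, so the absolute risk difference that the plan already promises should be standardised over the baseline distribution.

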**Patients with DM-ADRD experience DM over-treatment and under-treatment:** Diabetes care includes management of hyperglycemia, blood pressure, hyperlipidemia, and monitoring for microvascular and macro- vascular complications, using pharmacologic and non-pharmacologic (diet and exercise) management. DM-ADRD patients experience worse DM monitoring, poor non-pharmacologic treatment, and have worse metabolic outcomes than patients with DM alone. Under-treatment can potentially lead to symptomatic hyperglycemia such as polyuria, increased infections, weight loss and fatigue. Over-treatment can potentially lead to hypoglycemia, acute confusion, and health care utilization. VA research has shown potential over-treatment of hyperglycemia in veterans with ADRD and DM, ranging from over 50-63% of high risk veterans having HbA1c<7%. Hypertension in DM can be over- or under-treated; ACCORD and ADVANCE provide evidence for moderate management of hypertension in DM. Under-treatment of hypertension in DM has been well studied but there is VA evidence for hypertension over-treatment in routine clinical practice. Cholesterol management by statins in older DM patients was not specifically readdressed in ACCORD or ADVANCE. In Enhanced Quality In Primary Care for Elders with Diabetes-ADRD (EQUIPED-ADRD) we aim to target glycemic and blood pressure (BP) management based on ACCORD and ADVANCE evidence to decrease both over and under treatment. During the R21 phase of this study we developed consensus decisional guidance related to glycemia (measured as "HbA1c") and BP targets that also address monitoring for risks of complications, any new cholesterol recommendations, and non-pharmacological DM management with a goal of identifying safe, high quality management guidelines for DM-ADRD patients to be implemented in the R33 phase. These guidelines address 1) screening for cognitive impairment in older DM patients with out-of-desired range of HbA1c or BP but no ADRD diagnosis, 2) CG support, and 3) treatment based on CG preferences.

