### 3.2 Inclusion Criteria

Patient:

- 1) Patient must receive care at one of the INT or CON clinics.
- 2) Patient must be 65 years and older.
- 3) Patient must have DM diagnosis.
- 4) Patient must have documented cognitive impairment **or** an ADRD diagnosis (ICD-10 diagnosis in Epic).
- 5) Patient must have someone who is identified as a family or friend who provides caregiving assistance.

Caregiver:

- 1) Caregiver must have adequate knowledge of identified patient and/or participate in that member's healthcare decisions.
- 2) Caregiver must be English or Spanish speaking.
- 3) Caregiver must demonstrate capacity to consent to research participation.
- 4) Caregiver must be at least 21 years old.

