We will train intervention PMs in DM and ADRD management for INT clinics. Training will include one-on-one sessions with the mPI's and co-I's, suggested reading, shadowing relevant clinicians, such as social workers in the Alzheimer's Disease Center and geriatrics clinic, and other relevant activities. We expect training will require one month's duration with subsequent continuous learning activities that include continuing meetings with mPIs and co-I's and travel to national conferences.

**PM Activities.** The PM will reach out to eligible patients with diagnosed DM-ADRD (see section 4.3) and  $\geq 75$  year-old patients with over- and under-treatment of HbA1c/BP for cognitive screening using IQ-CODE as defined in the Guideline. For those with a positive screen, in coordination with the PCP, the PM will facilitate further cognitive evaluation. These patients will become part of the quality improvement intervention. The PM will begin telephonic assessment and DM management education of DM-ADRD patients around the time of the scheduled visit (either just before or just after). The PM will conduct a detailed psychosocial and needs assessment with each willing CG and assess the patient based on both a standardized assessment and clinical judgement. The PM will also engage those CGs who live far from the patient and who manage the patient remotely through paid home health aids (HHA). The CG psychosocial assessment will focus on diabetic management support and family dementia CG support providing referrals as needed to well established New York City programs. The PM will provide PCPs with evaluation data, DM-relevant care suggestions and facilitate PCP visits for care reassessment as clinically appropriate. The PM will assist the PCP and the dyad with developing individualized DM management targets and re-evaluating these targets over time. The PM will maintain dyad follow-ups and monitor patient-level data using EHR follow-up data as per usual clinical care, and an Epic-generated report for relevant issues. The PM will also address dyad goals and treatment preferences and assist with communicating these with the PCP. A key part of PM activity will be determining with each PCP their preferred method of communication (e.g., Epic messaging, order pending, periodic phone calls, etc).

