At primary care visits of DM patients with known ADRD or a positive cognitive screen, PCPs, coordinating with PMs, will proceed with DM management according to EQUIPED-ADRD Guidelines. PCPs will have PM information about CG stress, treatment preferences, and need for CG support referrals through the PM notes or Epic "in-basket" communications. PCPs will reassess as needed and encourage referrals. In patients with a positive cognitive screen, PCPs will follow guidelines for further cognitive evaluation per dyad preference. PCPs will have scripts to facilitate discussions, knowing that the PM will follow-up with the dyad after the visit. Clinic

workflow redesign is expected to be minimal. Providers will be alerted to the visit of relevant patients as described in the enrollment section and dyads will have an explanation of the EQUIPED-ADRD program through IRB approved brochures.

Over the 3 years of the study, the PM will continue to assist the dyad telephonically with DM-ADRD management support as clinically appropriate to meet management targets, communicating as needed with the PCP. EHR-generated reports on DM management will support intervention PCPs and PMs.

*Provider Feedback.* In the INT clinics, bi-annual reports will be given to providers and these will be discussed at bi-annual meetings which will be either by webinar or in person; in-person meetings will be held at least once a year. The provider-specific reports will detail DM-ADRD patients' medical management metrics such as numbers of caregiver referrals to community support, any changes in proportions of patients in range for HbA1c and BP, and the number of older adults with DM screened for cognitive impairment. Monthly patients lists will serve as periodic reminders of the quality improvement program. Other feedback and collaborative learning opportunities for INT clinic providers include quarterly "office hour" webinars with the mPI's and co-I's to review the reports and brainstorm opportunities for improvement.

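### Patients enter after clinic randomisation partly because HbA1c is out of range, and INT searches for them harder than CON; the primary model pre-specifies no baseline on-target term and no diagnosed-before-launch analysis is planned

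*Combined protocol and SAP*

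**What the plan says.** **Trigger.** Section 1.3 says that the guideline covers "screening for cognitive impairment in older DM patients with out-of-desired range of HbA1c or BP but no ADRD diagnosis". Section 4 (CON Clinics) gives CON providers the same trigger at age 75 and over.

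**Effort in INT (Section 4, INT Clinics).** Providers receive monthly lists that include "those 75 and older with DM who are out of range for HbA1c or BP". The panel manager reaches out to 75-plus "year-old patients with over- and under-treatment of HbA1c/BP for cognitive screening using IQ-CODE as defined in the Guideline" and helps arrange further evaluation of those who screen positive. Twice-yearly provider reports show "the number of older adults with DM screened for cognitive impairment". The section itself describes the monthly-list process as more intensive than what CON receives.

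**Effort in CON (Section 4, CON Clinics).** There is one initial list of DM-ADRD patients, encouragement at training to screen with the MiniCog, and a periodic EHR search by research staff for diagnosed patients.

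**Entry.** Both parts of Section 4 refresh the sample with new diagnoses over the three years. Criterion 4 of Section 3.2 reads "Patient must have documented cognitive impairment", or alternatively an ADRD diagnosis, so a screened patient can come to qualify. The CON text says that such patients become eligible for the evaluation. The INT text says that they join the quality improvement intervention; their entry to the evaluation is implied but not stated.

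**Expected numbers (INT only).** "Our preliminary data suggests 20-50 patients per INT clinic with DM-ADRD", and "about an equal number with DM without ADRD who will screen positive for cognitive impairment".

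**Analysis.** Section 7's primary model for HbA1c on target has treatment as the fixed effect of interest and practice as a random effect. The section holds that randomisation ought to make covariate adjustment unnecessary, and adds that factors which look unbalanced will be considered. Its planned sensitivity analyses concern missing data only. HbA1c status at month 0 is collected when available (Section 5.4, Measures), with no rule for which value counts.

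**The concern.** Randomising clinics balances the patients who are already there. It does not balance those recruited later by a process that the intervention itself drives. Here the process selects partly on the variable that becomes the primary outcome. If INT brings in proportionately more screen-detected patients, INT starts with fewer patients on target for reasons unrelated to the effect of care.

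What follows depends on how the outcome is read. On follow-up status, as Section 7 describes it, INT is handicapped: power is lost, or INT is made to look harmful. On change from baseline, which Table 1's description of the HbA1c outcome as a proportional change allows, the same patients regress towards the mean and INT is flattered. The plan does not rule out the second reading, and it fixes neither the adjustment nor the baseline value.

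**Working it through.** The plan gives no on-target rate, intracluster correlation (ICC), effect size or power for its target of 500 per arm, so there is no planned figure to reproduce.

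**1. How much late entry the plan expects.** Nine INT clinics with 20 to 50 diagnosed patients each give 9 × 20 = 180 to 9 × 50 = 450. That is 50 to 320 short of 500. (Section 3.1 mentions 20 practices but nine per arm; ten clinics would give 200 to 500.) Late entrants of any kind may fill the gap. With about equal numbers of diagnosed and screen-positive patients, about half of the INT programme pool is screen-detected. CON has no matching figure.

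**2. Bias in the follow-up comparison, with no treatment effect.** All inputs here are assumed: proportion on target p = 0.4 to 0.6; BP in range b = 0.5 to 0.7, independent of HbA1c; within-person HbA1c correlation ρ = 0.5 to 0.8 (bivariate normal, target a central band); gap d between the arms in screen-detected share.

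- On target at entry among triggered patients: q = p(1 − b)/(1 − pb).
- Shortfall at follow-up: p − f = (p − q) × (P11 − P01), where f is the on-target proportion at follow-up among triggered patients, and P11 and P01 are the chances of being on target at follow-up given on or off target at entry.
- Bias against INT = d × (p − f).

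| p | b | ρ | q | P11 − P01 | p − f | d = 0.25 | d = 0.50 |
|---|---|---|---|---|---|---|---|
| 0.4 | 0.5 | 0.5 | 0.20/0.80 = 0.25 | 0.449 − 0.367 = 0.082 | 0.012 | 0.3 points | 0.6 points |
| 0.6 | 0.7 | 0.8 | 0.18/0.58 = 0.31 | 0.765 − 0.353 = 0.41 (rounded) | 0.119 | 3.0 points | 6.0 points |

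These are the extremes of the grid. A 25-point gap means 50% in INT against 25% in CON; a 50-point gap needs 0% in CON. With equal shares d = 0 and the bias is 0. If half of the screen-detected patients come by referral unrelated to HbA1c or BP, the figures halve.

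**3. Change from baseline.** The bias is d(p − q)(1 − [P11 − P01]), towards INT. At d = 0.25 the two rows give 0.25 × 0.15 × 0.918 = 3.4 points and 0.25 × 0.29 × 0.59 = 4.3 points.

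**4. Which baseline value.** In large-sample calculations with an on-target baseline term (Monte Carlo error about 0.3 points):

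- Baseline is the triggering value: residual 0.3 points or less.
- Baseline is a separate earlier value: 0.3 to 1.8 points against INT at d = 0.25, and 0.6 to 3.6 at d = 0.50.
- CON screens only the more extreme half of out-of-range patients (shares 50% against 25%): with the triggering value, the baseline term leaves 0.6 to 2.4 points towards INT; adding entry route as well gives 0.8 to 3.2 towards INT.
- Patients diagnosed before launch only: within 0.3 points throughout.

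**5. Precision of the restricted set.** With m patients per clinic, the standard error ratio is √{[(1 + (m − 1)ICC)/m] ÷ [same at m = 500/9 = 55.6]}. At an assumed ICC of 0.02, m = 50 gives √(0.0396/0.0376) = 1.03 and m = 20 gives √(0.0690/0.0376) = 1.35.

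**The case against.** **The plan already handles part of this.** Section 7's list of characteristics to check is open-ended, includes the baseline of another outcome (TBQ), and allows unbalanced factors into the primary analysis. That stands in part. Simulating the rule as adjustment only when a chi-square test on baseline status gives p < 0.05, the bias is 0.8 points or less when the baseline is the triggering value, but up to 4.1 points when it is a separate value. The protection thus rests on a choice that the plan does not make. The balance test also ignores clinics: with a design effect of 1 + 55 × 0.02 = 2.1 it flags about 18% of balanced factors.

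**The trigger is common to both arms.** This stands. CON has the guideline, MiniCog training and Epic screening guidance, so a CON share of zero is an extreme, and equal shares would remove the bias.

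**Stronger readings that the documents do not support:**

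- A reader might infer an inflated chance of a false benefit. On follow-up status the excess rejections go against INT. In simulations at the most biased inputs, rejections favouring INT were 0.3% (25-point gap) and 0.1% (50-point gap), below the nominal 2.5%.
- A reader might set two panel managers at "each PM will have an anticipated 300 dyads", so 600, against 180 to 450 diagnosed patients and infer that 25 to 70% of INT is screen-detected. That sets one fixed caseload against both ends of a range, contradicts the same section's expectation of about equal numbers, and concerns programme caseload rather than the evaluated sample.
- A reader might take a baseline term alone as a full cure. Step 4 shows that it is not.

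**Conclusion.** The point holds as a gap in the design and analysis plan that should be fixed. Post-randomisation entry depends partly on the primary outcome variable, the search is more intensive in INT, and neither the primary model nor the planned sensitivity analyses address it.

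The direction is conditional: with a larger screen-detected share in INT, against INT on follow-up status and towards INT on change from baseline. The size is not established. The range of 0.3 to 3.0 points rests on the assumed on-target rate, correlation, BP rate and 25-point gap. About 6 points is an upper end that needs CON to have no screen-detected patients. It also presumes that INT screen-positives enter the evaluation, which the protocol implies without saying so. Confidence is high in the mechanism and medium in its importance.

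**What to change.** 1. **Section 7, primary model.** Pre-specify baseline HbA1c on-target status as a covariate and delete the statement that randomisation removes the need for adjustment. Define baseline by one rule for both arms relative to each patient's own entry, for example the last EHR value on or before the eligibility date, with a stated look-back window and a rule for missing values. Do not use a fixed calendar date: for patients who enter later, that is the separate earlier value which leaves bias. State that the outcome is follow-up status, not change, and align Table 1.

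2. **Sensitivity analysis.** Pre-specify an analysis restricted to patients whose DM-ADRD diagnosis in the EHR is dated before programme launch, found by the same query in both arms. It is needed because the baseline term can leave bias in either direction, depending on the baseline value used and on how selectively CON screens.

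3. **Entry.** State that screen-positive patients enter the evaluation by the same rule in both arms. Record entry route and report it by arm, counting IQ-CODE as well as MiniCog screens (Table 1 counts only the latter). Keep route out of the primary model, because the intervention affects it.

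**Cost.** SAP wording, a short protocol clarification and one recorded field; HbA1c and Epic data are already collected. Items 1 and 3 keep the full sample. Item 2 has a standard error about 3 to 35% larger at an assumed ICC of 0.02, on that sensitivity analysis only.

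The differing accounts of PCP list review and patient letters in Sections 5.1 and 5.2.1 are a separate point.
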